Mental health, dysfunctional eating pattern and weight trajectory in subjects undergoing bariatric surgery.

Sponsored by: Working Group of the SEEN (GOSEEN).

Study name: REGAINSEEN.

ID: HCB/2019/0090

Summary

Studying the mechanisms of weight regain (WR) may provide much-needed insight into sustained obesity management. The aim of this five-year, prospective, multicentre study is to evaluate the association among eating pattern (specifically maladaptive behaviours), certain psychological variables and weight trajectory in the short and long term after bariatric surgery (BS). The study will include 2 groups: 1.- Candidates to primary BS undergoing laparoscopic gastric bypass (LGBP) or laparoscopic sleeve gastrectomy (LSG) from September 2020 to September 2022. This group will be evaluated prior to surgery, at 4 months, 1 year, 3 years and 5 years after BS and 2.- A control group of subjects with obesity not candidates to BS matched with the intervention group for age, sex and BMI prior to BS. The primary variable will be: Body weight: total weight lost (%), excess weight lost (%), total weight regained (%), excess of weight regain (%). Information regarding the psychological and behavioural variables will be collected using questionnaires that have been validated in our setting and will be completed by the patients themselves online.

Introduction and update on the subject

Obesity is one of the main health problems today, with a prevalence of 20-30% in many European countries. Obesity is a chronic, progressive disease without cure that requires specific treatment for weight loss and continuous follow-up to avoid weight regain [1].

The objective of the treatment of obesity is to achieve significant sustained weight loss (WL), without undernourishment, and with an improvement in body composition and associated comorbidities. In this context, bariatric surgery (BS) is, at present, the only effective treatment to achieve marked and sustained WL in patients with severe obesity, typically yielding a long-term sustained weight losses of 25 to 35% of initial weight [2].

Although the mean data support the effectiveness of BS in the treatment of obesity, the magnitude of WL and the maintenance of weight reduction after BS notably differ among individuals, even among those undergoing the same surgical technique [3]. Data from the pivotal Swedish Obese Subjects (SOS) study show that the maximum WL after BS ranged between -95.5 and + 2.0 kg, and weight regain (WR) after nadir was between 0.0 and 51.4 kg[4]. This heterogeneity in weight trajectory leads some patients to present lower WL than expected and/or the recovery of an important amount of weight after nadir.

At present, it is recognised that the magnitude and maintenance of WL are important to the health results of BS. However, one of the main problems encountered is how to define insufficient WL and pathological WR after BS. A systematic review described that the most frequent definition used for insufficient WL after primary BS is a WL < 50% of the excess weight present prior to surgery with or without a body mass index (BMI) > 35 kg/m² at 18 months after surgery [5]. Thus, insufficient WL is not just the absolute WL but rather the deviation of WL from the result that is usually achieved after BS.

Likewise, in relation to the definition of WR, several studies have used different definitions based on kilograms, units of BMI, or percentage of excess WL regained after nadir or at different time points, including: regain of 10 kg, regain of 25% of excess WL; regain of 15% of initial WL; regain of 5 kg/m²; any WR with a BMI >35 kg/m² at nadir, at 18 months or 3-5 years post-BS [6]. Patients who show WR present a relapse of not only obesity but potentially also the co-morbidities which had remitted during the initial WL. In this case many require revisional surgery or a second procedure to re-achieve WL, either with RYGB, or another procedure such as duodenal switch at the expense of adding a malabsorptive component to the surgical process, which risks extra complications and a high rate of nutritional deficiencies (Annex 1).

The variability of WL or WR has been associated with a wide range of factors related to the surgical technique used, psychological factors, behavioural, dietetic factors, physical activity and comorbidities as well as biological factors which regulate food intake, energy storage and expenditure [7]. Variables such as previous weight, age and the type of surgery explain between 40-50% of the variance in WL, with the rest

remaining from the variance due to other variables. Although the influence of behavioural and psychological factors are of note in studies on WL after BS, the identification of predictors is not conclusive or has shown a weak relationship.

Despite recognition of the important influence of psychological factors on the results of BS at a weight level, there are no conclusive data to date [8]. The inconsistencies of the results seem to be due to different methodological factors such as the definition of the alterations, the evaluation methods used – clinical interview, psychometric tests, among others – the different time of evaluation, the time reference assessed and the willingness of the candidates to respond in the context of the request for BS. Recent systematic reviews have suggested a certain predictive capacity of some factors on weight results in regard to their influence on eating behaviour after BS (i.e. presurgical cognitive functioning, personality, mental health, some psychological variables and dysfunctional eating behaviours) [9][10]. Therefore, not all patients report benefits in the psychological domain. In some cases, previous pathology may recur or a new psychopathology may arise, impairing the quality of life and interfering in achieving the goals proposed. It is not known whether there is a characteristic profile in patients with insufficient WL or WR after BS.

Thus, within the context of the increasing use of BS it is essential to determine the causes for this variability in weight trajectory following BS and understand what factors have an impact on WR after BS in order to minimise and prevent them. As mentioned previously, behavioural and psychological factors are especially important and require the most attention in order to understand the influence these factors have on WR.

Objective:

The **objective** of this study is to evaluate the association among eating pattern (specifically maladaptive behaviours), certain psychological variables and weight trajectory in the short and long term after bariatric surgery.

Design

Five-year, prospective, multicentre study.

The study will include 2 groups:

- a) Candidates to primary BS undergoing laparoscopic gastric bypass (LGBP) or laparoscopic sleeve gastrectomy (LSG) from September 2020 to September 2022. This group will be evaluated prior to surgery (a period vulnerable to biases by the request for surgery that affect the answers to the questionnaires for fear of being contraindicated for surgery). The subjects of this group will be followed at 4 months, 1 year, 3 years and 5 years after BS.
- b) A control group of subjects with obesity not candidates to BS matched with the intervention group for age, sex and BMI prior to BS.

*The control group will be recruited by each investigator (10 subjects) and will be evaluated once. According to our casuistic, in order to be comparable with the REGAINSEEN

Versión 2, 07/03/2019

intervention group 80% should be women of 45 years of age with a BMI $> 40 \text{ kg/m}^2$. This group is needed to adjust for variables such as motivation, patient expectations related to surgery and the effect of surgery.

Inclusion criteria:

- Candidate to primary BS from 09/2010 to 09/2021.
- Subjects with obesity ($\geq 40 \text{ kg/m}^2$) not candidates to BS.
- Internet users.
- Primary BS: LGBP and LSG.
- Accept to participate in the study and provide signed informed consent.

Exclusion criteria:

- Second time and/or revisional BS.
- Pregnancy.
- Presence of intellectual impairment impeding the administration of the psychometric tools.
- Type 1 diabetes.
- Dyslexia.

Weight variables: definitions.

- a) The different weight variables will be calculated as follows:
 - Weight lost (kg): Pre-BS weight – weight at nadir.
 - Current weight lost: Pre-BS weight - current weight.
 - Ideal weight: weight corresponding to a BMI = 25 kg/m^2 .
 - Excess weight lost (%): $(\text{Pre-BS weight} - \text{current weight})/\text{excess weight} [(\text{pre-BS weight} - \text{ideal weight}) \times 100]$.
 - Total weight lost (%): $(\text{pre-BS weight} - \text{current weight}/\text{pre-BS weight}) \times 100$.
- b) To study WR the following variables will be calculated:
 - Total WR (%): $(100/(\text{pre-BS weight} - \text{weight at nadir})) * \text{weight regained (kg)}$.
 - Excess WR (EWR %): $[(\text{current weight} - \text{weight at nadir})/\text{excess weight}] \times 100$
 - Weight regained (Kg): current weight – weight at nadir.

Excess weight lost $> 50\%$, total weight lost $> 25\%$ and Excess weight regain $> 15\%$ will be considered as significant.

Psychological evaluation:

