- Social support evaluated by the evaluation protocol using the English Longitudinal Study of Ageing study. APGAR (including 5 questions).
- Quality of life evaluated using the Impact of Weight on the Quality of Life - Lite (IWQOL-lite) questionnaire including 31 questions.

Table 1: Questionnaires on hedonic response to food, addictive behaviour and mood state.

Hedonic response to food	Mood state, stress, negative emotions
DEBQ-external (10)	DEBQ-restraint and emotional (23)
Yale Food Addiction Scale II (25)	Positive and Negative Affect Schedule (PANAS) (20)
Binge eating scale (BITE) (33)	Barrat Impulsivity Scale (30)
Confounding variables	Alcohol Use Disorders Identification Test (AUDIT-4). Fagerström Nicotine Dependence Scale (6)
International Physical Activity Questionnaire (IPAQ) (7).	EPQR-neuroticism (23)
APGAR (5)	Hospital Anxiety and Depression Scale (14)
Quality of life evaluated with the Impact on Weight on the Quality of Life – lite questionnaire (IWQOL-lite) (31)	

Evaluation of food intake: The patients will also complete a registry of foods and drinks consumed over 3 days including a weekend day. It should include the type of food, cooking method, and portion size or weight. Afterwards, the total intake and by macronutrients will be analysed with the Diet Source software (Nestle Health Science. V4.0).

Primary variable:

Body weight: total weight lost (%), excess weight lost (%), total weight regained (%), excess of weight regain (%).

Data collection:

I. Additional information on demographic and anthropometric characteristics and on comorbidities both prior to BS and their evolution over time will be collected in an Excel datasheet designed with this objective and will include the following:

Centre: A number identifying each centre has been assigned starting at 1, with the first 9 numbers having a 0 before them.

REGAINSEEN

Versión 2, 07/03/2019

Code: To register the data of the patients a 5 digit code will identify each patient, with the first 2 numbers corresponding to the number assigned to the centre and the following 3 numbers will correspond to the number assigned to the patient upon entry in the study. For example, the first patient recruited in Hospital Clinic (corresponding to 04) will be assigned the code 001 so that the final code of this patient will be 04001. The code will be kept in each centre and confidentiality will be guaranteed by the investigator.

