Additionally, 100 controls not undergoing BS will be included and matched for age, gender and BMI with the objective of standardising the values in the scales. The ratio will be 1:4 for controls and patients undergoing BS, respectively.

Statistical analysis

The design and statistical analysis of the present study meet the recommendations of consensus documents in the literature [25]–[28], specially the TRIPOD statement [29]. A statistical analysis plan (SAP) will be elaborated [30] prior to finalisation of data collection and will provide an in depth description of the statistical methods to be used, the tables and figures that will be included in the statistical report as well as the

strategy to follow in the case of missing values [31], [32], and multiplicity [33] adapted to regulatory [34] and scientific recommendations [26].

Descriptive statistics will be used according to standard calculation methods [35]. To elaborate a predictive model to a determined time, logistic regression models will be used [36]–[39]. For time variables up to a determined event, survival analysis techniques will be used. The function of survival as well as the median of time to the event (confidence interval of 95% [CI 95%]) will be estimated using the Kaplan-Meier method. Estimations of risk will be made with the classical [40] and extended [41] Cox proportional hazards model. Covariables will be tested for the assumption of proportional hazards. Initially all the possible covariables will be analysed in a univariate analysis, and factors with $p < 0.1$ will be included in a multivariate model. All the variables not selected for inclusion ($p \geq 0.1$) will, in turn, be checked in the final model to determine whether their inclusion would improve adjustment of the model by a p value < 0.1 or a value less than Akaike. Continuous variables will be tested as continuous linear variables, categorical variables (that is, quartile and predefined for clinical reasons) or continuous non-linear variables based on previously published literature, clinical value and goodness-of-fit models.

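### The protocol says pre-surgery questionnaire answers are biased by fear of refusal, but it does not time the baseline survey after acceptance, plans no analysis of the bias, and has a control group that cannot adjust for it.

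*Combined protocol and SAP*

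**What the plan says.** Design item a) gives the baseline timing as "This group will be evaluated prior to surgery" and in the same sentence describes that time as "a period vulnerable to biases by the request for surgery that affect the answers to the questionnaires for fear of being contraindicated for surgery". The Introduction lists "the willingness of the candidates to respond in the context of the request for BS" among the reasons why earlier studies disagree.

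Design item b) defines the comparison group: "A control group of subjects with obesity not candidates to BS matched with the intervention group for age, sex and BMI prior to BS". It adds "The control group will be recruited by each investigator (10 subjects) and will be evaluated once" and gives the purpose: "This group is needed to adjust for variables such as motivation, patient expectations related to surgery and the effect of surgery". The Sample size section gives these controls another purpose, "with the objective of standardising the values in the scales".

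Under Psychological evaluation, patients complete the questionnaires themselves online. The Ethical Committee section says the consent sheet will stress confidentiality. The Statistical analysis section describes regression, survival and mixed models, and promises a later SAP that will cover methods, missing values and multiplicity. Response bias at baseline is not mentioned there.

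**The concern.** The study's objective is the association of eating pattern and psychological variables with weight trajectory. The baseline scores are the only pre-surgical measure of those variables. The sponsor states that they are distorted and cites the same problem to explain conflicting literature. Yet a site that follows the plan exactly may send the survey at the point when concealment is most likely.

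Three things are at stake:
- **Within-cohort associations.** If patients hide symptoms to differing degrees, the score-to-weight association is distorted.
- **Confounder adjustment.** Scales treated as confounders, such as the anxiety and depression scale, are answered under the same pressure, so adjusting for them may leave residual confounding.
- **Score contrasts.** Candidate-control differences, and changes from baseline if the questionnaires are repeated, would include the distortion.

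The statement that the controls provide adjustment may lead a reader to think the problem has been handled.

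**Working it through.** **1. The plan's own figure.** Inputs from Sample size: standardised difference 0.281, two-sided 5%, power 80%, 400 completers, 10% loss. The plan does not state a split; an even one is assumed.
- n per group = 2 × (1.960 + 0.842)² / 0.281² = 198.8, so 199 per group and 398 in all.
- Noncentral-t power at 200:200 is 0.800.
- Enrolment = 400 / 0.9 = 444.4, so 445.

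The figures reproduce with an even split inside the surgical cohort. They make no allowance for distorted scores.

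**2. What the controls can identify.** Let δ be the true mean difference between candidates and controls, and b the mean shift due to the request for surgery. The observed difference is δ + b. Every surgical patient is a candidate and no control is, so one observed quantity carries two unknowns. Matching on age, sex and BMI does not separate them. One assessment gives no change over time, and controls have no surgical weight trajectory. Data collection also lists control weights at 4, 12, 36 and 60 months, which conflicts with a single evaluation and must be reconciled. Extra weights would not repair questionnaire answers.

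**3. What standardising to controls does.** The rescaled score is Z = (X − m)/s, with the same m and s for every patient. Correlation with the outcome is unchanged by such a transformation. A simulation (400,000 patients, true correlation −0.140) shows this:

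| Assumed reporting | Before | After rescaling |
|---|---|---|
| Uniform shift of 0.5 SD | −0.140 | −0.140 |
| Shift varying between patients | −0.130 | −0.130 |
| Above-average scores halved, plus random error of SD 0.5 | −0.115 | −0.115 |

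Most of the fall in the last row comes from the added error. Halving alone leaves a covariance with the true score of 0.75 and a variance of 0.585, so the correlation with the true score is 0.75/√0.585 = 0.98 and the association is −0.140 × 0.98 = −0.137. The table shows that rescaling repairs nothing. It does not estimate the size of the bias.

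**4. Illustrative loss of power.** Suppose a share λ of baseline score variance is true signal and the rest is independent error. Comparing mean scores between two halves of the cohort, the observed effect is 0.281 × √λ.

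| λ (assumed) | Effect (SD) | Power, 200:200 |
|---|---|---|
| 1.0 | 0.281 | 0.80 |
| 0.9 | 0.267 | 0.76 |
| 0.8 | 0.251 | 0.71 |
| 0.7 | 0.235 | 0.65 |
| 0.6 | 0.218 | 0.58 |

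No λ stands in the documents. The formula describes random error, whereas the feared mechanism is directional concealment. If concealment were related to later weight, the association could move either way.

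**The case against.** The strongest reply is that much of the safeguard may lie in text not available here. The consent pages are not in the reviewed copy, the survey's opening screen is not shown, and the Ethical Committee section promises emphasis on confidentiality. This stands: it cannot be said that patients are not reassured. But confidentiality of data differs from a statement that answers play no part in the decision on surgery, so the point is to confirm it.

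A reader might also infer that survey answers are exposed because "The code will be kept in each centre and confidentiality will be guaranteed by the investigator". The documents do not support that. The code is described for the Excel datasheet and not as a survey key, and holding it locally is ordinary pseudonymisation.

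A reader might infer that the controls were assigned to correct fear of refusal. The plan does not say so. It names motivation, expectations and the effect of surgery. The criticism is that non-candidates cannot adjust for surgery-related motivation or expectations either.

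It is also fair that body weight, the primary variable, is not self-reported on these questionnaires, and that a uniform shift leaves within-cohort associations intact. If the questionnaires are repeated after surgery, those scores offer a comparison less exposed to the fear. The plan does not clearly say they are repeated, nor how they would be used. The promised SAP could add a sensitivity analysis, but it cannot change when the baseline answers were given.

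**Conclusion.** The concern holds as a gap between a bias the protocol admits and a design that leaves it in place. The survey may be completed before the decision is known, and no analysis addresses the consequence. The control group cannot adjust for surgery-related motivation or expectations, and could not remove this bias. That conclusion rests on the design and needs no assumed figure.

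The harm to the main association depends on under-reporting that varies between patients, which is plausible but not quantified in the documents. A uniform shift would matter only for candidate-control and before-after score contrasts. The range of 0.267 to 0.218 SD and 0.76 to 0.58 power rests on assumed reliabilities, an assumed even split and a random-error model. It should not be read as the study's actual loss of power. Nor do the documents show that candidates will look healthier than controls; that would need the size and direction of b.

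**What to change.** 1. In Design item a), state that the baseline survey link is sent after the patient has been told of acceptance for surgery and that the survey is completed before the operation. Record decision status at completion, so that early responses can be identified.
2. Confirm that the survey screen and consent sheet say the answers play no part in the decision on surgery; add the sentence if it is absent.
3. In Design item b), limit the controls' role to reference values for the scales, in line with the Sample size section.
4. State whether the questionnaires are repeated after surgery. If they are, specify in the SAP a sensitivity analysis that uses those scores, noting that they may also reflect the effect of surgery itself.

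The cost is one timing rule, one recorded field, a sentence to check and a reworded claim. Sites must time the survey link, and some fear may remain after acceptance. Candidates who are refused would not be surveyed, but the cohort is already defined as patients undergoing surgery. The rule has to be in force before each patient is surveyed, because a pre-surgery baseline cannot be retaken after the operation.

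### Controls need a BMI of at least 40 but surgical candidates have no stated BMI limit, so the BMI matching fails for any surgical patient below 40

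*Combined protocol and SAP*

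**What the plan says.** The Design section describes the second group as follows: "A control group of subjects with obesity not candidates to BS matched with the intervention group for age, sex and BMI prior to BS". The Sample size section repeats the requirement for 100 controls, "matched for age, gender and BMI with the objective of standardising the values in the scales", at one control to four surgical patients.

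The Inclusion criteria admit controls as "Subjects with obesity ($\geq 40 \text{ kg/m}^2$) not candidates to BS", a line that runs into the next item as "not candidates to BS. - Internet users". For the surgical group the same list gives only "Candidate to primary BS from 09/2010 to 09/2021" and "Primary BS: LGBP and LSG", besides internet use and consent, which apply to everyone. Neither the inclusion nor the exclusion list gives a BMI figure for surgical candidates.

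A note under Design says that each investigator recruits 10 controls, evaluated once. Citing the sponsor's own case experience, it says that for comparability with the "intervention group 80% should be women of 45 years of age with a BMI" above 40. So the sign is at-least in the criteria and strictly-above in the note. The note also says that the controls serve to adjust for motivation, expectations of surgery and the effect of surgery itself.

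No matching method, caliper or banding is stated, and the BMI distribution of surgical candidates is not given.

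**The concern.** Two instructions for choosing controls do not fit together. One ties the controls to the surgical patients' BMI. The other sets a floor, and a profile from past cases, that applies to controls whatever the enrolled surgical patients look like. An investigator can fill 10 places to the profile and satisfy the note without having matched to anyone.

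This matters because of what the controls are for. They supply reference values for the questionnaires and a contrast meant to separate candidacy and surgery from obesity itself. Some of the scales, weight-related quality of life (IWQOL-Lite) above all, plausibly vary with BMI; that is an assumption, not a figure from the protocol. For two-group comparisons of continuous variables, the Statistical analysis section names Student's t test or a rank-based alternative. It names no BMI adjustment for the control comparison. Matching is therefore the only stated protection there against reading a BMI difference as an effect of candidacy or surgery.

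**Working it through.** **1. The plan's own figures.** Allowing for 10% loss, 400 / 0.90 = 444.4, so 445 patients. For a standardised difference of 0.281 at two-sided 5% and 80% power, n per group = 2 × (1.960 + 0.842)² / 0.281² ≈ 199. With 200 against 200, a t test detects 0.2808. The stated figures therefore reproduce as a comparison of two halves of the 400 surgical completers. Neither the controls nor BMI enter, so this point leaves the sample size unchanged.

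**2. The rules side by side.**

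| Rule | Surgical group | Controls |
|---|---|---|
| Inclusion criteria | no BMI figure | at least 40 |
| Control note (Design) | described as the group to resemble | above 40, in a profile of 80% women aged 45 |
| Summary, Design, Sample size | the group matched to | matched on age, sex and BMI |

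A surgical patient below 40 is eligible as written; a control below 40 is not. The first and third rows can both be met only if no surgical patient is below 40.

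**3. How large the gap could be.** The surgical BMI mean m and SD s are assumptions; the documents give neither. Assume a normal distribution and put a = (40 − m)/s.

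- Share of surgical patients below 40 = Φ(a); number = 445 × Φ(a).
- Excess mean BMI of controls, if they follow the surgical distribution above 40 = s × φ(a) / (1 − Φ(a)).

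| Assumed mean, SD | Below 40 | Of 445 | Excess control BMI, kg/m² (in SD) |
|---|---|---|---|
| no patient below 40 | 0% | 0 | 0 |
| 48, 4 | 2.3% | 10 | 0.22 (0.06) |
| 46, 5 | 11.5% | 51 | 1.10 (0.22) |
| 45, 6 | 20.2% | 90 | 2.12 (0.35) |
| 43, 6 | 30.9% | 137 | 3.05 (0.51) |
| 42, 7 | 38.8% | 172 | 4.38 (0.63) |

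For the middle case, a = (40 − 45)/6 = −0.833, Φ(a) = 0.202, and 445 × 0.202 ≈ 90.

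**4. What the gap reaches.** If standardising means z = (x − control mean) / control SD, with one mean and SD for everyone, each surgical patient's score is shifted and scaled alike. Correlations and test statistics within the surgical group do not change; a regression coefficient changes only in its unit. What can move is the level of the standardised scores and any control-versus-surgical contrast.

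**The case against.** The strongest reply is that the floor was set to mirror the expected surgical population. The control note says, from the sponsor's casework, that a BMI above 40 is what makes controls comparable, and nowhere do the documents say that patients below 40 will be enrolled. With 100 controls for 445 patients, matching may well be to a group profile, in which case the absence of an individual partner for one patient is not in itself a failure.

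Much of this stands. A reader might infer from the floor that the reference values come from a heavier group. The documents do not support that as a fact. A lower limit on controls does not by itself raise their mean: controls clustered just above 40 could average the same as, or less than, the surgical group. The excess in the table needs both surgical patients below 40 and controls spread like the surgical group above it.

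What does not stand is that the note settles the matter. It describes an expectation and sets no surgical entry limit. It is also ambiguous: the 80% may cover sex alone, with 45 years as a typical age, or the whole profile, which leaves 20% of the expected group outside it on sex, age or BMI. Nor does group matching remove the problem. Controls cut off at 40 can be made to agree in mean BMI with a group that extends below 40, but not in distribution.

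It is also fair that weight, height, age and sex are recorded in both groups, so adjustment is possible. But it is not planned for this comparison, and where the groups do not overlap it would be extrapolation.

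**Conclusion.** The inconsistency is in the text and needs no assumption: a floor for controls, none for surgical candidates, and a requirement to match on BMI. Its consequence is conditional. It is nil if no surgical patient is below 40. Over the assumed range (normal BMI, mean 42 to 48, SD 4 to 7) between 10 and 172 of 445 patients would lack a BMI-comparable control, and the controls would be 0.2 to 4.4 kg/m² heavier only if they follow the surgical distribution above 40.

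A reader might also take this as a threat to the study's main objective. It is not. Associations of eating pattern and psychological variables with weight trajectory within the surgical group are unaffected, provided that standardisation uses one common control mean and SD. The difference between the two signs is minor, but it should be removed.

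**What to change.** Reconcile the control floor with the matching rule.

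- **Preferred:** replace the floor and the fixed profile with frequency matching to the surgical patients actually enrolled, on coarse sex, age and BMI bands, balanced across the whole study. Full cross-classified cells within each centre would not work: two sexes × two age bands × three BMI bands is 12 cells, against 10 controls per investigator.
- **If the floor is kept:** restrict the standardisation and the control comparison to surgical patients with a BMI of at least 40, and say so.
- **In either case:** adjust the control-versus-surgical comparison for baseline BMI, age and sex, state the matching method, and use one sign throughout.

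The cost is amendment wording and a study-wide tally of bands. No extra controls and no new data are needed. Under the first option some controls are chosen later, once the enrolled mix is known. Under the second the comparison uses fewer surgical patients, but the 100 controls dominate its precision. By the normal approximation, the difference detectable with 80% power is 2.80 × √(1/100 + 1/445) = 0.31 SD with all 445. In the worst assumed case (445 − 172 = 273 patients) it is 2.80 × √(1/100 + 1/273) = 0.33 SD.

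### Total and excess weight lost (%), two of the four primary variables, are printed with misplaced brackets and cannot be calculated as written; the intended formulas are evident and the correction is textual

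*Combined protocol and SAP*

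**What the plan says.** The Primary variable section lists four percentages, beginning "Body weight: total weight lost (%), excess weight lost" and continuing with total and excess weight regained. The section Weight variables: definitions sets out how each is to be derived:

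- The line for "Total weight lost" reads: "Total weight lost (%): $(\text{pre-BS weight} - \text{current weight}/\text{pre-BS weight}) \times 100". The round bracket closes after the division.
- Excess weight lost: "Excess weight lost (%): $(\text{Pre-BS weight} - \text{current weight})/\text{excess weight} [(\text{pre-BS weight} - \text{ideal weight}) \times 100". The square bracket closes after the 100.
- Total regain: "Total WR (%): $(100/(\text{pre-BS weight} - \text{weight at nadir})) * \text{weight regained (kg", closing normally.
- Excess regain: "Excess WR (EWR %): $[(\text{current weight} - \text{weight at nadir})/\text{excess weight}] \times 100", with the 100 outside the bracket.

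Ideal weight has its own line ("Ideal weight: weight corresponding to a BMI" of 25 kg/m²). Excess weight does not; its only expression is the bracket inside the excess weight lost formula. The same section then marks as significant an excess weight loss above 50%, a total weight loss above 25% and an excess regain above 15%. The Data collection section says the derived weight variables will be calculated from the recorded weights.

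**The concern.** These lines are operative rules for primary variables, not background text. Followed as printed, neither loss formula gives a percentage to which its cut-off can be applied.

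For total weight lost, the printed expression subtracts a ratio from a weight in kilograms, so differences between patients would mostly reflect how heavy they were before surgery. The study's objective is to relate psychological and eating variables to weight trajectory, and such a variable would distort comparisons between patients.

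For excess weight lost, the printed line can be taken literally in two ways, and they lead to opposite classifications against the 50% cut-off.

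**Working it through.** The documents report no value calculated from these formulas, so there is no figure to reproduce. Each formula is evaluated as printed and then with the evident intended brackets.

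**Inputs.** P = pre-surgery weight, C = current weight, N = nadir weight, I = ideal weight, E = excess weight. The formulas, cut-offs and ideal BMI of 25 come from Weight variables: definitions. Individual weights and heights are not given. The assumed example is P = 120 kg, C = 84 kg, height 1.65 m. Then I = 25 × 1.65² = 68.06 kg and E = 120 − 68.06 = 51.94 kg.

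**Total weight lost (%).**
- As printed: (P − C/P) × 100 = (120 − 84/120) × 100 = (120 − 0.7) × 100 = 11,930.
- Intended: [(P − C)/P] × 100 = 36/120 × 100 = 30.
- With no loss (C = 120), as printed: (120 − 1) × 100 = 11,900.
- In general: 100P − 100C/P = 100P − 100 + 100(1 − C/P), which is 100P − 100 plus the true percentage. Each extra kilogram before surgery adds 100 points.
- Range, assuming heights of 1.55 to 1.80 m, BMI 40 to 55 and losses of 0 to 35%: about 9,510 to 17,755. With no loss it is already 9,510 to 17,720, a spread of 8,210 points from starting weight alone, against at most 35 points from true loss. Every patient exceeds 25.
- Because 100P − 100 is fixed for a patient, changes between visits within one patient would still be right. Levels, cut-offs and comparisons between patients would not.

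**Excess weight lost (%).**
- Intended: [(P − C)/E] × 100 = 36/51.94 × 100 = 69.3.
- Bracket read as the denominator: 36/(51.94 × 100) = 0.0069. This is 10,000 times too small, because the result is divided by 100 instead of multiplied by it. Even C = 0 gives only 120/5,194 = 0.023, so nobody reaches 50.
- Bracket read as a multiplier: (36/51.94) × (51.94 × 100) = 3,600, that is, 100 × kg lost. Any loss above 50/100 = 0.5 kg passes the cut-off.

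**Regain formulas.** Same patient, with assumed N = 80 kg and C = 90 kg.
- Total regain as printed: 100/(120 − 80) × 10 = 25.0%.
- Excess regain as printed, with E = P − I: 10/51.94 × 100 = 19.3%. The 15% cut-off corresponds to 0.15 × 51.94 = 7.8 kg regained, so it works.
- Excess regain if the stray × 100 were carried into E: 10/5,194 × 100 = 0.19%. This is 100 times too small, and about 779 kg of regain would be needed to reach 15%.

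**The case against.** The strongest reply is that these are typographic slips with only one sensible correction each. The variables are labelled as percentages, the cut-offs are 25% and 50%, the Introduction gives typical long-term losses of 25 to 35% of initial weight, and it describes insufficient loss relative to preoperative excess weight. A natural reader takes the square bracket as explaining excess weight and the × 100 as the conversion to a percentage. A total weight loss of 11,900% in a patient who lost nothing would be noticed at once. Weights in kg and height are recorded, so nothing is lost, and the Statistical analysis section promises a SAP in which the formulas can be put right. All of this stands, and it limits the practical harm. It does not make the printed rules correct.

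The formulas were also read from a PDF, so a bracket could have moved in conversion. The two regain formulas in the same list came through intact, which makes that less likely, but a check against the source is sensible.

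A reader might infer two stronger points that the documents do not support:

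- **That the 15% regain cut-off also fails.** Its own formula is correctly bracketed and works with excess weight as pre-surgery minus ideal weight. It fails only if the misplaced × 100 is imported into the meaning of excess weight. That is a strained reading, because the regain formula already has its own × 100.
- **That the binary outcomes of the logistic models and GLMM would be constant.** The Statistical analysis section names no such outcomes. The cut-offs are only described as significant, and the evolution of the weight variables is assigned to a mixed model for repeated measurements as continuous data. Nothing shows that the formulas will be programmed literally.

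**Conclusion.** The point holds for total weight lost and excess weight lost. As printed, total weight lost is inflated by 100 × pre-surgery weight − 100, about 9,500 to 17,700 points over the assumed range, and its 25% cut-off separates no one. Excess weight lost is either 10,000 times too small, so that no one passes 50%, or equal to 100 × kg lost, so that almost any loss passes. The regain formulas are sound, although excess regain relies on a term with no definition line of its own.

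The sizes rest on assumed heights and weights, but the algebraic identities do not. The conclusion also assumes that the brackets in the source PDF are as they appear here. Since the intended formulas are evident and the raw data are collected, this is a necessary but low-cost correction, not a threat to the study.

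**What to change.** Check the brackets against the source PDF. Then, in Weight variables: definitions and in the SAP, write:

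- Excess weight (kg) = pre-BS weight − ideal weight, on a line of its own.
- Total weight lost (%) = [(pre-BS weight − current weight)/pre-BS weight] × 100.
- Excess weight lost (%) = [(pre-BS weight − current weight)/excess weight] × 100.

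Leave both regain formulas as printed, with excess regain using the excess weight defined above. Make the change before derivation code is written. The cost is three lines of text, with no new data and no change to the design.
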